8.1 Participant Risks

Participation in this study may be associated with minor risks or safety concerns. The potential risks of this study fall into 4 categories: 1) those related to research participation; 2) those related to testing procedures; 3) those related to study powder; 4) those related to depressive symptoms. The risks are outlined for each category below:

Minor Risk of Participation in Research: With any study, risk of breach of confidentiality is possible since we are collecting personal health information.

Minor Risk of Testing Procedures: It is possible that participants may find the questionnaires tedious or may be uncomfortable being asked about sensitive topics like suicidality. The participants may also experience pain or bruising that results from the blood draw. With any puncture of the skin, there is an increased likelihood for infection, although this is minor. Participants may also find it inconvenient to fill out diet records and/or collect 24 hour urine samples.

Minor Risk Related to Study Powder: We do not anticipate any major risks for the participants with consumption of the freeze dried blueberry. However, the proposed intervention will provide an older adult with 30% of the recommended daily intake of dietary fiber. One may experience side effects that commonly occur with increased dietary fiber consumption if the individual typically consumes relatively low amounts of dietary fiber.

Risk Related to Depressive Symptoms: It is possible that individuals with depressive symptoms may progress in symptom severity during the study period. Although we do not anticipate a change to a more severe category of depression, we recognize that our proposed population of older adults with prevalent depressive symptoms are already predisposed to development of more severe depressive disorders. Importantly, our population of interest is also more likely to experience suicidal ideation.

8.2 Risk Minimization

We will attempt to minimize the identified risks as specified below:

Risk Minimization of Participation in Research: To minimize the risk of breach in confidentiality, all primary study data will be recorded with computer tablets on electronic case report forms (CRF) or as digital files generated from laboratory equipment. All data recording will be in accordance with procedures and guidelines outlined in the study's Manual of Procedures (MOP) authored by the study team. Participant confidentiality will be maintained by recording subject data using a unique subject identifier. Identifiable data, such as contact information and medical record numbers, will be recorded and stored separately from the clinical study data. Any paper-based study material and any identifiable data will be kept separate in a locked file cabinet accessible by authorized study staff only. Only the study staff directly responsible for the data collection and the safety of the participant will have access to identifiable information. All electronic CRF data will be stored securely in an electronic data capture and management system. Raw electronic instrumentation data will be organized and saved on a private network file dedicated to the research project. Only those listed on the approved IRB protocol will have access to subject data. Subject data will be coded and locked in a file cabinet in a locked office. Identifying information will not be used during discussion, presentation or research publication. All documents and electronic data will be archived for a minimum of three years, or as required by the IRB and federal regulations, after the completion of the clinical trial. The study will be registered at clinicaltrials.gov.

The Hinda and Arthur Marcus Institute for Aging Research employs the Research Electronic Data Capture (REDCap) system for data capture and data management operations. REDCap is a full-featured clinical trials data management system (DMS) accessible to data entry and data analysis workstations using secure Web technologies. While REDCap can be used to collect virtually any type of data (including 21 CFR Part 11, FISMA, and HIPAA-compliant environments), it is specifically geared to support online or offline data capture for research studies and operations. REDCap is developed and maintained by Vanderbilt University in cooperation with REDCap Consortium members, including HRC. HSL hosts and maintains a dedicated instance of REDCap for use across our research enterprise. Each research project is provided separate workspace in which all of the study data are stored in a MySQL relational database on the private corporate network behind several firewalls and located physically within the HSL data center.

Risk Minimization of Testing Procedures: The majority of the testing procedures will be questionnaire based. Participants will be advised that they can refuse to answer any of the questions. Participants will be permitted to rest between studies to prevent fatigue. To minimize the risk of being uncomfortable during questionnaires on sensitive topics like suicidality, only trained research staff will administer the questionnaires. Research staff will be trained to administer them in a calm, welcoming demeanor and will reassure the participants that the assessment(s) can stop at any time.

To avoid any risk associated with blood draws, only individuals with trained phlebotomist skills will draw blood using standard, sterile safety procedures to minimize risk of infection. Unless performed at the participant's home/residence or other HSL housing facility, blood draws will be done at our study clinic that resides in Hebrew SeniorLife, which is a functioning hospital. Thus, in the rare case a participant needs additional care that the study team is not qualified to provide, the individual will be transferred immediately to the adjacent hospital.

To avoid any inconvenience with collecting urine/filling out dietary records, all required equipment will be provided to the participant. If requested reminders for when to collect the urine sample/fill out diet records can be arranged.

Risk Minimization of Study Powder: Individuals with allergies to blueberries will not be included in this study to avoid any adverse effects/allergic reactions. We anticipate that the blueberry powder will be well-tolerated by participants since it consists of a food (i.e., blueberries) that are regularly consumed. Regardless, every visit we will ask participants about any complaints or adverse events that are directly related to the study intervention. We plan to track diarrhea, gas, bloating, abdominal pain, constipation etc. Since our intervention provides only ~30% of the recommended intake of daily fiber, we do not anticipate this amount will result gastrointestinal distress, if consumed alone. Nevertheless, symptoms of gastrointestinal distress will be captured at each visit and appropriately addressed by the study team. [name], who has a PhD in Nutrition, will consult with participants on their experience with the fiber and reconcile any gastrointestinal stress. If a participant develops a health problem or a potential health problem (in addition to the ones outlined below), the PI will be notified ASAP.

Risk Minimization of Depression Severity: Although we do not anticipate a change to a more severe form of depression, we recognize that our proposed population of older adults with prevalent depressive symptoms are already predisposed to development of more severe depressive disorders. The level of depression will be evaluated and monitored at all visits to proactively monitor participant safety. If at any time during the study an individual's assessments indicate they have progressed to a more severe forms of depression, then specific safety protocols will be followed (e.g., notifying the PI). Our population of interest is also more likely to experience suicidal ideation, which will also be monitored at every visit to identify any individuals, who may need psychiatric care outside this study. If the participant is deemed to be dangerous or at imminent risk of harm, study staff will contact emergency services (i.e., #911) for immediate medical assistance.

General Risk Minimization: The proposed protocol requires 4 visits over approximately 5 weeks and therefore imposes a moderate amount of participant burden with respect to time and effort. Our institute has a strong track record of successful clinical research requiring similar participation, and retention has been high in these projects. The Clinical Research Laboratory at the Marcus Institute is located near a cafeteria and rest room, and is equipped with comfortable seating, a TV, movies, books, and magazines to keep individuals occupied during rest periods. Several additional strategies will be employed to minimize participant burden and maximize adherence to the protocol. We will:

- Develop a personal relationship between participants and members of the staff.
- Schedule appointments at convenient times with familiar staff.
- Explain to participants all aspects of their participation and follow up. We will demonstrate and practice study procedures before beginning data collection.
- Provide reminders of all appointments and follow-up phone calls.
- Include personal notes in the participant's data file to remember events in the life of the participant; these can be commented on at the next visit (e.g., birthday, birth of a grandchild).
- Provide snacks and lunch during all visits.
- Provide transportation for all visits, if required.
- Provide valet or dedicated on-site parking spaces.
- Compensate participants for visits.

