Diet Records: 1-day and 3-day diet records will be filled out by participants, documenting the amount and types of foods/beverages ate during the allotted time. Records will be reviewed by research staff for accuracy and completeness. Records will be entered into a dietary analysis program (e.g., Nutrition Data System for Research) to estimate dietary intake of nutrients.

Visit 1 (1st Baseline Visit, approximately 60 minutes)

Prior to their baseline visit, individuals will be asked to also fast 12 hours prior to their scheduled visit. They will come to our clinical research laboratory, have a blood draw (up to 20 mL of plasma and/or serum) and be asked questionnaires about their lifestyle (e.g., smoking habits), current social network, sleep habits, positive/negative affect, and relevant symptoms (e.g., gastrointestinal symptoms, pain etc.). For safety depressive symptoms (via CES-D/CESD-R and PHQ-9) and suicidal ideation will be assessed (via P4SS). Height, weight, and vitals will be measured. They will turn in their 1-day diet record and their 24-hour urine sample. After participants will be randomly assigned to either consume a 24 g dose (equivalent to ~ 1 cup) or a 48 g dose (equivalent to ~2 cups) of freeze-dried blueberry powder mixed in water. Participants will be asked to consume their assigned dose in the morning for the next 3 days, while recording diet records and compliance during those 3 days. Immediately after they consume the last dose of their intervention powder (e.g., Day 3), they will begin to collect a 24 hour urine sample for the day prior to their next study visit.

Lifestyle: Alcohol use, smoking status, etc. will be collected via self-report.

Social Network: Subjective perception of social support and connectedness will be evaluated using a validated questionnaire.

Sleep Quality and Quantity: Sleep will be evaluated by a self-report questionnaire and/or sleep log diary.

Height: Height will be measured at the baseline visit using a stadiometer.

Weight: Weight will be measured using a digital Health-o-meter scale.

Vital Signs (e.g., seated blood pressure) will be measured at the baseline visit. After 3-5 minutes of rest, seated blood pressure will be measured twice with an automated cuff.

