Blood (up to 20 mL) will be collected by a trained phlebotomist using sterile procedures. Blood will be processed and stored at -80 degree C for future analyses. Batch analyses of relevant inflammatory markers (e.g., C-reactive protein, interleukins) will be measured by a reputable lab (e.g., the Metabolic Phenotyping Lab at the University of Connecticut).

Relevant Symptoms: Information on relevant symptoms including gastrointestinal distress, appetite, pain etc., will be collected by self-report.

Compliance: Compliance with our dietary intervention will be evaluated throughout the study. Participants will be asked to log consumption of their powder and keep all of their used powder packets. At the study visit, participants will return all unused and used powder packets to estimate number of intended doses that were consumed.

Mood Questionnaires: Given that our population of interest is more likely to develop more severe forms of depressive symptoms and experience suicidal ideation, both will be monitored at in-person visits. Depressive symptoms will be monitored by the Patient Health Questionnaire-9 (PHQ-9)[35] and the CES-D/CESD-R[28, 29]. These are validated questionnaires to evaluate severity of depressive symptoms and depression level. We will also assess the participant's attitude via validated self-report questionnaire, Positive and Negative Affect Scale (PANAS).

Visit 2 (1st Follow-Up Visit, approximately 60 minutes)

Participants will turn in their 3-day diet records, compliance logs, all packets, and their urine sample, as well as have a fasted blood draw (up to 20 mL of plasma and/or serum). They will also be asked to complete the same questionnaires that were administered at Visit 1 (except for lifestyle behaviors), as well as measure their vitals and weight. Participants will then enter a second washout period to avoid consuming flavonoid-rich foods for 2 weeks.

Just as they did before the 1st Baseline Visit, participants will be asked to collect a 24 hour urine sample and begin filling out their 1-day diet record as described before.

Visit 3 (2nd Baseline Visit, approximately 60 minutes)

This Visit will be exactly like Visit 1 (i.e., fasted blood draw, questionnaires, measurements of vitals etc. except for height measurement and evaluation of lifestyle behaviors). However participants will be asked to consume the other amount of powder for 3 days.

Visit 4 (2nd Follow-Up Visit, approximately 60 minutes)

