This Visit will be exactly like Visit 2 and will be the last Visit of the study.

A summary of study visits and assessments is provided in the table below. Given that a primary goal of this pilot study is feasibility, we will allow for flexibility for the administration of some assessments at visits, as long as these changes do not impede the scientific interpretation.

Table 1. Assessments by Visit

[figure not shown]
	Telephone Pre- Screening	Pre-study Visit	Visit 1	Visit 2	Visit 3	Visit 4
Telephone Screening Script	X					
Depressive Symptoms ¹	X		X	X	X	X
Medical History	X	X				
P4 Suicidality Screener		X				
Informed Consent		X				
Diet Records	X		X	X	X	X
24-hr Urine Collection		X		X	X	X
Lifestyle			X			
Social Network and Sleep Habits			X	X	X	X
Height			X			
Vital Signs and Weight			X	X	X	X
Mood Assessment ²			X	X	X	X

Symptoms	X	X	X	X
Blood Draw	X	X	X	X
Compliance		X		X

¹ via Center for Epidemiological Depression Scale (CES-D) and CES-D revised (CESD-R)

²Includes the Patient Health Questionnaire-9 and Positive and Negative Affect Scale

Figure 1.

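### Table 1 schedules the P4 suicidality screen once, before dosing, while the section 5.1 visit text and section 8.2 commit to monitoring suicidal ideation at in-person visits or every visit

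*Combined protocol and SAP*

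**What the plan says.** Section 8.2, on minimising the risk from worsening depression, says: "Our population of interest is also more likely to experience suicidal ideation, which will also be monitored at every visit". It gives the purpose as finding participants who may need psychiatric care outside the study.

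Section 5.1 is consistent with this in its narrative:

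- **Pre-intervention visit:** ideation is evaluated with the P4, a 4-item questionnaire.
- **Visit 1:** "For safety depressive symptoms (via CES-D/CESD-R and PHQ-9) and suicidal ideation will be assessed (via P4SS".
- **Mood Questionnaires paragraph:** of worsening depressive symptoms and suicidal ideation, it says "both will be monitored at in-person visits".
- **Visit 2:** "They will also be asked to complete the same questionnaires that were administered at Visit 1", with only the lifestyle items excepted.
- **Visit 3:** "This Visit will be exactly like Visit 1", with only height and lifestyle excepted.
- **Visit 4:** "This Visit will be exactly like Visit 2 and will be the last Visit of the study".

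Table 1, at the end of section 5.1, differs. Its row "P4 Suicidality Screener" has one mark, in the pre-study column. Footnote 1 defines the depressive-symptoms row as CES-D and CESD-R. Footnote 2 defines the mood-assessment row as PHQ-9 and PANAS. Neither includes the P4.

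The sentence introducing Table 1 adds: "we will allow for flexibility for the administration of some assessments at visits, as long as these changes do not impede the scientific interpretation".

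**The concern.** The P4 is the only instrument the protocol names for suicidal ideation: in the exclusion criteria (section 3.3), at the pre-intervention visit and at Visit 1. The Visit 1 sentence separates the tasks, giving CES-D/CESD-R and PHQ-9 to depressive symptoms and the P4 to ideation. The marks for depressive symptoms and mood at Visits 1 to 4 in Table 1 therefore cannot be taken to stand in for it.

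Visit checklists and case report forms are often built from a schedule table. Forms built from this one would contain no dedicated ideation screen at Visits 1 to 4, including both post-dosing visits (2 and 4). The safeguard in 8.2 works only if ideation is detected, and section 8.3 provides no DSMB or safety officer, so detection rests on visit procedures and the principal investigator. The flexibility sentence does not help: its only stated limit is scientific interpretation, so it does not clearly protect a safety screen from being left out.

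**Working it through.** The plan gives no figure to reproduce. The check is a comparison by visit, then a count and a timeline.

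**Comparison**

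| Source | Pre-intervention | Visit 1 | Visit 2 | Visit 3 | Visit 4 |
|---|---|---|---|---|---|
| Table 1, P4 row | marked | blank | blank | blank | blank |
| 5.1 overview table | self-harm questions named | mood questionnaires, P4 not named | same | same | same |
| 5.1 visit text | P4 named | P4 named | as Visit 1 | as Visit 1 | as Visit 2 |
| 5.1 Mood Questionnaires | monitored | monitored | monitored | monitored | monitored |
| 8.2 | monitored | monitored | monitored | monitored | monitored |

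Visit 1 is the clearest conflict, because the text names the same instrument that Table 1 leaves blank. It does not depend on how the word monitored is read. The exceptions listed for Visits 2 and 3 do not remove the P4. The overview table is ambiguous for Visits 1 to 4, since mood questionnaires could include ideation items, so it is not counted on either side. The telephone pre-screen is also left out of the count: 5.1 refers to in-person visits and 8.2 to every visit.

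**Count**, assuming the P4 is used wherever the text has ideation monitored and all 5 participants complete:

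- Table 1: 1 screen per participant; 1 × 5 = 5.
- Text: 1 + 4 = 5 screens per participant; 5 × 5 = 25.
- Absent from Table 1: 25 − 5 = 20, and 20/25 = 80%.

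**Timeline.** Inputs are the two 2-week washouts (5.1), 3 days of powder (5.1) and follow-up on day 4 of each dosing cycle (6.1). Visit 2 is taken as 3 to 4 days after Visit 1, and Visit 4 likewise after Visit 3.

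- Pre-intervention visit: day 0.
- Visit 1: 0 + 14 = day 14.
- Visit 2: 14 + 3 to 4 = day 17 to 18.
- Visit 3: 17 to 18 + 14 = day 31 to 32.
- Visit 4: 31 to 32 + 3 to 4 = day 34 to 36.

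This agrees with the participation time of about 5 weeks (35 days) in section 3.4. Under Table 1 the 34 to 36 days after the single screen contain no further P4. Under the text the longest interval between screens is 14 days, the length of each washout.

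**The case against.** The strongest reply is that this is an omission from a summary table, not two competing safety plans. The visit text, the mood paragraph and 8.2 all point the same way, and no passage says that ideation is screened only once. Table 1 also has other apparent slips: it shows urine collection at the pre-study visit and not at Visit 1, where the sample is handed in, and diet records at the telephone pre-screen. Some rows may have been displaced in conversion from PDF. Practice will follow a manual and case report forms that are not available here, so the harm is conditional. The counts assume Table 1 is followed literally. Other safeguards remain: depression scales at Visits 1 to 4, adverse-event questions at each visit of the intervention period, exclusion of people with current ideation, and a procedure for imminent risk.

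Much of this stands as to weight. The figures measure the disagreement between the two schedules; they do not predict missed cases. The exact column of the mark should be checked against the protocol itself, although one mark cannot represent five visits whichever column it is in. The remaining safeguards limit the consequence, but the protocol does not say that any of them replaces the P4. None of these points removes the contradiction, and no passage says which source prevails.

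**Conclusion.** The concern holds. The protocol gives two incompatible schedules for its only named ideation screen: 1 administration per participant in Table 1 against 5 in the text, with 34 to 36 days unscreened against a longest gap of 14. The figures rest on the P4 being the instrument throughout, on all 5 participants completing, and on visits falling at the planned times.

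The gap is confined to dedicated ideation screening; measurement of depression severity at Visits 1 to 4 is the same on either reading. No estimate or test in section 6.1 is affected. It should be corrected because it concerns a safety commitment the protocol itself makes, and because the correction is cheap.

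**What to change.** Before enrolment, or now if enrolment has begun:

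1. Reconcile the P4 row and footnote 2 of Table 1, the 5.1 overview table, the 5.1 text for Visits 1 to 4, and section 8.2, so that all give the same ideation-screening visits and name the instrument.
2. State whether the flexibility sentence before Table 1 applies to this screener.
3. Check the case report forms and the manual of procedures against the reconciled schedule.

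Which schedule applies is for the sponsor and IRB to decide. The cost is protocol wording and a form check. If the every-visit text governs, forms built from Table 1 would gain a 4-item questionnaire at up to four further visits per participant.

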8.3 Quality Assurance and Safety Monitoring

The Principal Investigator (PI) will assume primary responsible for ensuring participants' safety on a daily basis. Since this is a single-site, phase 1 pilot study, without high risk, our study will not require an official Data and Safety Monitoring Board (DSMB) or a Safety Officer. However, to ensure and monitor participant safety, any adverse event will be documented.

8.4 Adverse Event Collection and Reporting

Any adverse or serious adverse events will be logged using forms either provided by or modeled after the forms that are provided by the NIA Clinical Research Toolbox. The baseline visit will mark the beginning of when any potential adverse or serious adverse events could occur/be collected. All other AE's will be collected as a part of the parent study.

Adverse Event Definition and Categorization

An adverse event is any untoward medical occurrence in a participant, whether or not it is causally related to the study. An adverse event can therefore be any unfavorable and unintended sign (including an abnormal laboratory finding, for example), symptom or disease temporally associated with the study. Adverse events will be recorded on the appropriate case report forms and source documents. The PI and/or trained staff member will evaluate all adverse events as to their severity and relation to the study. The severity of adverse events will be graded as follows:

Mild: Awareness of a sign or symptom but easily tolerated.

Moderate: Discomfort sufficient to cause interference with usual activity or to affect clinical status.

Severe: Incapacitating with inability to do usual activity or to significantly affect clinical status.

Life Threatening: The participant was at immediate risk of death from the adverse event as it occurred.

The Investigator will also assess the relationship of any adverse event to the study, based upon available information, using the following guidelines:

0 = Unlikely: No temporal association, or the cause of the event has been identified

1 = Possible: Temporal association, but other etiologies are likely to be the cause; however, involvement of the study procedures cannot be excluded.

2 = Probable: Temporal association, other etiologies are possible, but not likely.

To determine the attribution and temporal association of an adverse event we will consider the following:

- 1) Whether the participant reports they have experienced the same symptom prior to the study intervention.
- 2) Whether the symptom occurred and resolved within 24 hours of taking the study intervention.

The PI and study staff will consider the symptom according to the conditions stated above and determine temporality as per clinical judgment.

Definition of a Serious Adverse Event

A serious adverse event is any experience that results in any of the following outcomes:

- Death
- Is life-threatening
- Inpatient hospitalization or prolongation of hospitalization

A persistent or significant disability/incapacity. Important medical events that may not result in death, be life-threatening, or require hospitalization may be considered a serious adverse event when, based upon appropriate medical judgment, they may jeopardize the patient or participant and may require medical or surgical intervention to prevent one of the outcomes listed in this definition. We do not anticipate any Serious Adverse Events with our intervention.

Adverse and Serious Adverse Event Reporting

There is a potential for adverse events and incidental findings during this study. A structured questionnaire asking about adverse events will be assessed during each visit of the intervention period. However, when any adverse has been identified, the study team will take appropriate action necessary to protect the study subject and then complete the Adverse Event form that will be modeled after the form provided by the NIA Clinical Research Toolbox. This form requires Principal Investigator review and signature. After review by the Principal Investigator any adverse event will be reported to the IRB as appropriate.

AE's that 1) are unexpected in nature, severity, or frequency, 2) are possibly, probably, or definitely related, and 3) suggests that the research places participants at a greater risk of harm than previously known or recognized, will be reported to the IRB as appropriate (e.g., within 2 weeks of the event).

If a serious event occurs, it will be brought immediately to the attention of the Principal Investigator, who will discuss the event with the co-investigators and together decide if immediate treatment is necessary. If such treatment is necessary, the PI, co-investigators, or the study staff will coordinate such treatment in an appropriate hospital or urgent care setting, contact the primary care physician, and notify the IRB. A Serious Adverse Event form that is modeled after the one provided by the NIA Clinical Research Toolbox will be completed, which requires Principal Investigator review and signature. If an AE is defined as a SAE, the Principal Investigator will be notified as soon as the event is known about. Routine reporting of any SAEs will be reported to the IRB within as appropriate.

Unanticipated problems or adverse events will be reported according to Advarra's IRB written guidelines for interventional studies. Unanticipated problems and serious adverse events that are probably, possibly, or definitely related to the study will be reported as soon as possible from the time of learning of the event, but reported within 10 days to Advarra's IRB per Advarra IRB guidelines. Advarra will be provided a written report submitted and a submission of the incident via the eIRB system. This form will record any adverse symptoms and/or study protocol deviations. Study staff will reference a Subject Safety Event Reporting Decision Chart provided and updated regularly by Advarra to determine whether an event needs to be reported to the Advarra IRB.

All other adverse events/study incidents will be logged on an Adverse Event log and reported to the IRB following the appropriate reporting times as defined by the Advarra IRB.

For less serious or incidental findings the Principal Investigator will speak with the participant about the finding. If necessary, the PI may suggest appropriate follow-up with their clinical provider and/or provide a letter describing the findings and need for follow-up.

Any adverse events that take place during testing will be reported to the PI and recorded in the database. The PI will have ultimate responsibility for monitoring participant safety in the trial. The investigators will be responsible for reviewing each adverse event in a timely fashion, and reporting all incidents to the appropriate regulatory agencies according to written guidelines.

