8.5 Participant and Study Stopping Rules

Participant Stopping Rules: If a participant experiences any adverse event that is deemed "severe" as outlined in §8.4 (Adverse Events Collection and Reporting) their continuation in the study will be determined by the PI. Additionally, if a serious adverse event (SAE) occurs, it will be carefully reviewed by the study team. Any report of a serious adverse event (SAE) that is thought to be directly related to the study products or study procedures, will result in the participant's discontinuation from the study.

Study Stopping Rules: Similar to the participant stopping rules, all serious adverse events (SAE) will be carefully reviewed by the study team to determine if study termination is warranted.

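### The only timing criterion for attributing adverse events requires resolution within 24 hours as well as onset, so under daily dosing persistence counts against relatedness

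*Combined protocol and SAP*

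**What the plan says.** Section 8.4 rates each adverse event on a three-level relatedness scale. The bottom level reads "0 = Unlikely: No temporal association, or the cause of the event has been identified". The next begins "1 = Possible: Temporal association, but other etiologies are likely to be the cause", and the top level, Probable, also presupposes temporal association.

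The section then explains how the rating is reached: "To determine the attribution and temporal association of an adverse event we will consider the following". Two items follow. The first is "Whether the participant reports they have experienced the same symptom prior to the study intervention". The second is "Whether the symptom occurred and resolved within 24 hours of taking the study intervention". The principal investigator and staff are to consider the symptom in the light of these two items and settle temporality by clinical judgment.

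Three other parts of the protocol bear on this:

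- **Schedule.** Sections 5.1 and 5.2 have the powder taken each morning for 3 days in each period. A 24-hour urine collection starts after the last dose, and the follow-up visit is the next day.
- **Expected symptoms.** Section 8.1 anticipates side effects of added fiber. Section 8.2 states: "We plan to track diarrhea, gas, bloating, abdominal pain, constipation etc".
- **Use of relatedness.** The reporting text in 8.4 makes relatedness a condition of the 10-day report to the IRB for serious events and unanticipated problems. Section 8.5 discontinues a participant after a serious adverse event "that is thought to be directly related to the study products or study procedures".

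**The concern.** Temporal association normally asks whether an event began at a plausible time after exposure. Whether it then went away is a separate fact. With repeated dosing, a symptom that continues while exposure continues is, if anything, compatible with a causal link. The second item in 8.4 merges the two questions, so a symptom that began promptly after a dose but lasted gets the same answer as one with no timing link at all.

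The item covers every adverse event, not only gastrointestinal complaints. The definition of a serious adverse event in 8.4 includes lasting disability, which by its nature cannot have resolved within 24 hours. Read as written, the criterion counts against relatedness in the cases where the rating has most consequence. Section 8.3 provides no monitoring board or safety officer who might notice the pattern.

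**Working it through.** The plan gives no figure to reproduce. The check traces the criterion through the dosing schedule and then through the rating scale.

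**Inputs.** Doses are once daily for 3 days (5.1, 5.2), taken here as hours 0, 24 and 48. The window is 24 hours (8.4). The symptom times below are assumed for illustration, since the protocol gives none.

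**Step 1: the onset half.** The 24-hour windows after the three doses run from 0 to 24, 24 to 48 and 48 to 72 hours. Together they cover 0 to 72 hours without a gap. Any symptom starting in that span has started within 24 hours of some dose, so the onset half cannot separate one such symptom from another.

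**Step 2: the resolution half.** The protocol does not say which dose starts the clock. Two readings are possible.

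| Illustrative symptom | Clock from the dose before onset | Resolution timed from the last dose |
|---|---|---|
| Hour 6 to hour 60 | 60 − 0 = 60 h, more than 24: not met | 60 − 48 = 12 h: met |
| Hour 54 to hour 84 | 84 − 48 = 36 h, more than 24: not met | 84 − 48 = 36 h: not met |

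For the first symptom, the second reading times onset from dose 1 and resolution from dose 3. The text neither permits nor forbids this.

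**Step 3: the boundary.** Any symptom still present after hour 48 + 24 = 72 fails on both readings. The follow-up visit falls at about that hour, so a symptom still continuing beyond that visit fails, even if it began shortly after the last dose.

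**Step 4: from criterion to rating.** The other listed item, prior experience of the symptom, says nothing about timing against a dose. The second item is therefore the only stated timing test. Not meeting it counts, on the natural reading, against temporal association. Without temporal association neither Possible nor Probable is available, and the remaining level is Unlikely.

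**Step 5: from rating to use.** An event rated Unlikely does not meet the relatedness condition of the 10-day IRB route in 8.4. The participant rule in 8.5 also turns on relatedness, but in looser words that are not tied to the three-level scale.

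**Scale of exposure.** There are 5 participants × 2 periods = 10 courses of 3 days. The protocol gives no expected event rate or duration, so the number of affected events cannot be calculated.

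**The case against.** The strongest reply is that the two items are things to consider and that temporality itself is left to clinical judgment. Nothing states how a negative answer to the second item is scored. This stands. A reader might infer that any symptom lasting beyond 24 hours must be rated Unlikely, and the text does not say so. The criterion pushes the rating and does not fix it. Still, it is the only timing guidance the assessor receives, and nothing prompts the assessor to set it aside.

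A reader might also infer that every symptom longer than 24 hours is affected. The unstated reference dose rules that out: the 54-hour symptom above (hour 6 to hour 60) passes on one reading.

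Nor does relatedness alone decide IRB reporting. The general rule in 8.4 requires three things together: that the event be unexpected, related, and suggestive of more risk than was known. Fiber-related complaints are already described in 8.1 and 8.2, so they would usually fail the first condition whatever their relatedness score. Other events are still logged and reported on the IRB's own timelines. In 8.5, severe events go to the principal investigator and all serious events are reviewed, regardless of relatedness.

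Finally, one might conclude that the safety findings would be biased towards none. The documents do not support that. Events are recorded whether or not they are causally related, symptoms are collected at all four clinic visits, and Section 6.1 plans no analysis restricted to related events. The counts by dose survive. What can be wrong is the label attached to them.

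**Conclusion.** The point holds as a minor flaw in the attribution rule. Under this schedule, the only stated timing criterion distinguishes events by persistence and not by onset, and it does so in the wrong direction. Symptoms outlasting the last dose by more than 24 hours are pushed towards Unlikely on either reading. Those that persist across doses but end sooner are pushed that way only if the clock starts at the dose before onset.

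The consequence is mislabelled relatedness in the tolerability data and possible mis-scoring of a persistent serious event or unanticipated problem, for which relatedness is a condition of the 10-day IRB report. The practical effect is likely to be small with 5 participants and 3 days per dose.

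This rests on two assumptions: that a negative answer to the second item counts against temporal association, and that assessors generally follow the listed items when they exercise judgment. If assessors routinely disregard the resolution half, the effect disappears.

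**What to change.** In 8.4 and on the adverse event form, remove resolution within 24 hours as a condition of temporal association. Assess association on onset relative to dosing in that period, and state which dose is the reference. Record duration and resolution as separate fields, so that the information is kept but does not drive the relatedness score.

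The cost is about one line in 8.4 and small changes to the form, with the change-log entry and staff briefing that Chapter 9 requires for any amendment. No dose, visit, stopping rule or analysis changes. The downside is that a few more events may be rated Possible.
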